6.6. Interim Analyses and Data Monitoring

An SMC meeting to review safety data is planned between Cohort 4 and Cohort 5. Safety data, including AEs; SAEs; clinical laboratory results (CHEM, HEM, COAG, and UA); VS, and 12 lead ECGs will be presented by cohort. Reasons for subjects who terminate the study early or discontinue treatment will be presented for all cohorts. The SMC may also review safety data by Dose Group in the closed session or *ad hoc* meetings as requested. An interim analysis of PK data is planned following the completion of Cohort 3. The interim PK report will only show PK data in aggregate and will not include any potentially unblinding information. The interim PK analysis will be conducted on the PK Analysis Population and will present

concentration and estimated PK parameter results for both specimen types by Dose Group and analyte. Further details of the interim PK analysis are provided in the Interim Noncompartmental PK Analysis Plan for the study [6].

6.7. Multicenter Studies

This is a single-site study.

6.8. Multiple Comparisons/Multiplicity

This is a Phase 1 FIH study with multiple primary endpoints. Because analyses of primary endpoints are descriptive rather than hypothesis tests, no adjustments for multiple testing are planned.

7. STUDY SUBJECTS

7.1. Disposition of Subjects

Screened subjects who were ineligible for enrollment in the study (screen failures) or eligible but not enrolled will be summarized by inclusion and exclusion criteria ([Table 11](#)). Enrolled subjects who were ineligible for inclusion in analysis populations will be summarized by reason for subject exclusion and Dose Group

([Table 10](#)). Individual listings of subjects who were excluded from the Safety Population or a PK Analysis population will be listed ([Listing 5](#)).

Subject disposition will be summarized ([Table 9](#)), showing the number of subjects who were screened, enrolled and randomized, received study product, completed all planned PK blood draws, completed all planned PK urine samples, completed final study visit, participated in the fast and fed cohorts (for Cohort 3 and Cohort 6), and terminated early.

Subjects who discontinued dosing or terminated early from the study will be listed ([Listing 2](#)).

A flowchart displaying the disposition of study subjects will be included ([Figure 2](#)). This figure will present the number of subjects screened, enrolled, lost to follow-up, and analyzed by Dose Group.

7.2. Protocol Deviations

A summary of subject-specific protocol deviations will be presented by deviation category, deviation type, and Dose Group ([Table 8](#)). This table will provide both the number of subjects and the number of deviations for each deviation category and deviation type. All subject-specific protocol deviations and non-subject-specific protocol deviations will be listed in [Listing 3](#) and [Listing 4](#), respectively.

8. EFFICACY EVALUATION

There are no efficacy endpoints for this trial.

9. SAFETY EVALUATION

All safety analyses will be performed using the Safety Population and will be presented by Dose Group. Placebo subjects enrolled in Cohort 3 that continued on to Cohort 6 will be counted separately for each dosing period, as detailed in Section [3.3.2](#).

Any medical condition that is present at the time that the subject is screened will be considered baseline and not reported as an AE, unless it worsens in severity or increases in frequency during the study. The denominators for proportion values will be indicated within the table or table header. AEs will be summarized for the number of subjects who experienced an AE and the number of events by Dose Group and Medical Dictionary for Regulatory Activities (MedDRA®) category. Toxicity grading scales for clinical adverse events are provided in All reported AEs will be included in the summaries and analyses.

Clinical laboratory, VS, and ECG results will also be used to assess safety. Results from these assessments will be graded by severity and presented in tables and figures by Dose Group for each post baseline timepoint. The analysis timepoints that will be summarized are presented in [Table 7](#). The most extreme severity grade observed after dosing will be summarized (Maximum Severity Post Baseline) and will include results from unscheduled visits. For tabular displays of clinical laboratory, VS, and ECG results by parameter, the maximum severity across all parameters within each category (CHEM, HEM, COAG, UA, VS, and ECG) will be included and summarized by timepoint (Any Parameter). CHEM, WBC (in COAG), and VS parameters will be displayed by event direction (increase or decrease).

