### 5.1.2 Subject Exclusion Criteria

1. has a chronic condition that may increase risk to subject or interfere with endpoint assessment (e.g., liver disease, kidney disease, immunodeficiency).
2. Chronic condition diagnosed within 90 days of the screening visit
3. Unstable chronic disease\* within 6 months of the screening visit  
     \*as defined by need for medical intervention that lead to a change in medications and/or required hospitalization, surgery/procedure, or ED/urgent care visit
4. History of psychiatric condition that has required hospitalization in the last 5 years or patient is considered unstable by study investigator
5. Any condition that in the opinion of the Investigator could significantly impact drug absorption, distribution, or elimination;
6. Any out of normal range laboratory value\* at screening or enrollment ([Section 8.1](#) and [Appendix B](#)).

\*A laboratory value that is Grade 1 (with the exception of ALT, AST, Total bilirubin, hemoglobin or serum creatinine) will be allowed if not considered to be clinically significant by the investigator.

7. Abnormal ECGs. See [Section 7.1](#) Clinical Evaluations for exceptions;
8. Electrocardiographic QTcF interval  $>430$  msec for males and  $>450$  msec for females at Screening;
9. Positive test for antibodies to HIV-1, HIV-2, HBsAg, or HCV;
10. Positive urine drug test. The drugs that will be screened for includes amphetamines, barbiturates, cocaine, opiates, cannabinoids, phencyclidine, and benzodiazepines.

- 
11. Female subject of childbearing potential who is pregnant\*, lactating, or planning to become pregnant during the study period or 3 months after the final dose of study product;  
\*Having a positive serum pregnancy test at the Screening Visit or any other specified time point prior to the dose of study product.
  12. Received any study product in a clinical trial within 30 days prior to Screening;
  13. Admitted or documented illicit drug use or alcohol abuse within 6 months prior to Screening or during their participation in the trial;
  14. Consumed alcohol within 72 hours of Day -1, until after the visit to the CRU on Day 14 or have a positive alcohol test at Screening or on admission to the CRU;
  15. Tobacco\* use within 90 days prior to the Screening Visit or while a subject is enrolled in the study OR A positive urine drug test for cotinine;  

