### 10.5.2 Clinical Safety Labs, Vital Signs, and Electrocardiograms

Baseline for clinical safety labs, vital signs, and ECGs will be defined as the last result obtained before the dose of study product. Clinical safety labs, vital signs, and ECGs results and changes from baseline will be summarized by treatment arm and visit. Clinical safety labs and vital signs will be graded ([Appendix B](#)) and summarized by severity, treatment arm, and visit. If triplicate ECG measurements were performed at the same visit, then baseline is the mean value of the measurements for the visit closest to, but before, administration of study drug. Similarly, for analyses of change from baseline, mean values will be used in the case of replicate measurements at a single visit post-baseline.

Treatment-emergent abnormal laboratory test results will be identified. Treatment-emergent abnormal laboratory tests are tests for which the result was not graded as mild or worse at baseline but graded as mild or worse after dosing. Laboratory tests graded as mild at baseline,

but moderate or worse any time after dosing will also be regarded as treatment-emergent abnormal laboratory test results.

ECG measurements will include heart rate, RR interval, QT interval, QTcF interval, PR interval, and QRS duration. Baseline for ECG measurements is defined per protocol as the value pre-dosing on Day 1. Change from baseline will be summarized descriptively by regimen at each scheduled evaluation. QTc results will be summarized categorically according to the ICH Guideline E14 “Clinical Evaluation of QT/QTc Interval Prolongation and Proarrhythmic Potential for Non-Antiarrhythmic Drugs” (October 2005).

- QTcF >450 ms;
- QTcF >450 ms, males only;
- QTcF >470 ms, females only;
- QTcF >480 ms;
- QTcF >500 ms;
- QTcF increases from baseline by at least 30 ms but less than 60 ms;
- QTcF increases from baseline by at least 60 ms.

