- All HEM results, including unscheduled visits, will be presented in [Listing 13](#). Abnormal results will be presented in [Table 24](#).
- All COAG results, including unscheduled visits, will be presented in [Listing 14](#), Abnormal results will be presented in [Table 25](#).
- All UA results, including unscheduled visits, will be presented in [Listing 15](#). Abnormal results will be presented in [Table 26](#).

All Screening results will be listed for each subject by Dose Group and visit:

- Serology results ([Listing 16](#)).
- Urine toxicology and alcohol urine results ([Listing 17](#)).
- Serum human chorionic gonadotropin (hCG) and pregnancy testing results ([Listing 18](#)).

Laboratory results will be summarized in tables and figures:

- Proportion of subjects with abnormal laboratory results by parameter, Dose Group, and timepoint for CHEM ([Table 27](#)), HEM ([Table 30](#)), COAG ([Table 33](#)), and UA ([Table 36](#)).
- Proportion of subjects with mild, moderate, or severe laboratory results by parameter, Dose Group, and timepoint for CHEM ([Table 28](#)), HEM ([Table 31](#)), COAG ([Table 34](#)), and UA ([Table 37](#)).
- Summary statistics of change from baseline by parameter, Dose Group, and timepoint for CHEM ([Table 29](#)), HEM ([Table 32](#)), COAG ([Table 35](#)), and UA ([Table 38](#)). UA character results (i.e. “1+”) will be excluded from change from baseline summaries.
- Graphical presentation of change from baseline at scheduled visits by Dose Group, and timepoint for each parameter as a series of box plots.
 - CHEM parameters will be presented beginning at [Figure 5](#) and continuing through [Figure 28](#).
 - HEM parameters will be presented beginning at [Figure 29](#) and continuing through [Figure 38](#).
 - COAG parameters will be presented for PTT ([Figure 39](#)), PT ([Figure 40](#)), and international normalized ratio ([Figure 41](#)).
 - UA parameters presented include specific gravity ([Figure 42](#)) and pH ([Figure 43](#)).

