14.3.4 Abnormal Laboratory Value Listings (by Subject)

Table 23: Listing of Abnormal Laboratory Results – Chemistry

[Implementation Note: This listing is included in the table shells document, as it is included in the body of the CSR. This listing includes all abnormal Chemistry results (laboratory results outside of the normal range defined in the protocol). Normal chemistry results for other parameters that occurred on the same visit as the abnormal result will not be listed. There is a separate, complete listing of all Chemistry results in Appendix 3. In the Laboratory Parameter column, indicate the units in parentheses after the parameter, e.g., Sodium (mEq/L). This listing is not color-coded, but the severity should be included in parentheses after the result, e.g., 133 (Mild). Results that are outside the normal range but not mild, moderate, or severe will have (ONR) as the severity included after the result. Results that meet grading criteria of mild, moderate, or severe but which are not treatment emergent (not worse than baseline, as described in Section 9.6) will be shown as “ONR”.

Sort order: Dose Group, Subject ID, Timepoint, and Parameter.

Dose Group order: 40 mg Fasted, 80 mg Fasted, 160 mg Fasted, 160 mg Fed, 320 mg Fasted, 640 mg Fasted, Placebo.

Parameter order: albumin, glucose, blood urea nitrogen, potassium, calcium, sodium, chloride, total protein, creatinine, triglycerides, total cholesterol, low-density lipoprotein, high-density lipoprotein, total carbon dioxide, creatine phosphokinase, phosphorus, alkaline phosphatase, aspartate aminotransferase, alanine aminotransferase, total bilirubin, direct bilirubin, magnesium, gamma-glutamyl transferase (GGT), serum cortisol]

Dose Group	Subject ID	Sex	Age (years)	Timepoint	Date of Assessment	Laboratory Parameter (Units)	Result (Severity)

Table 24: Listing of Abnormal Laboratory Results – Hematology

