[Implementation Note: If there is not at least one Mild, Moderate, or Severe event for a Dose Group within a parameter, then only the Maximum Severity Post Baseline row will be shown for that parameter. Only include chemistry parameters with grading criteria in the protocol. Toxicities representing an increase in the laboratory result will be summarized separately from decreases. For example, there will be one row for “Sodium, Decrease” and another for “Sodium, Increase”. Subjects who received VT-1598 in both Cohorts 3 and 6 will be included separately for each dosing period in the Any Dose Group. Similarly, subjects who received placebo in both Cohorts 3 and 6 will be included separately for each dosing period in the Placebo Dose Group.]

Parameter order: albumin, glucose, blood urea nitrogen, potassium, calcium, sodium, chloride, total protein, creatinine, triglycerides, total cholesterol, low-density lipoprotein, high-density lipoprotein, total carbon dioxide, creatine phosphokinase, phosphorus, alkaline phosphatase, aspartate aminotransferase, alanine aminotransferase, total bilirubin, direct bilirubin, magnesium, gamma-glutamyl transferase (GGT), serum cortisol. Decrease parameters will always be listed before increase parameters, if applicable]

Dose Group	Timepoint	N	Mild	Moderate	Severe
			n (%)	n (%)	n (%)
Chemistry - Any Parameter					
Any Dose	Baseline	x	x (x)	x (x)	x (x)
	Maximum Severity Post Baseline	x	x (x)	x (x)	x (x)
	Day 4	x	x (x)	x (x)	x (x)
	Day 7	x	x (x)	x (x)	x (x)
	Day 14	x	x (x)	x (x)	x (x)
	Day 21	x	x (x)	x (x)	x (x)
40 mg Fasted	Baseline	x	x (x)	x (x)	x (x)
	...	x	x (x)	x (x)	x (x)
80 mg Fasted	Baseline	x	x (x)	x (x)	x (x)
	...	x	x (x)	x (x)	x (x)
160 mg Fasted	Baseline	x	x (x)	x (x)	x (x)
	...	x	x (x)	x (x)	x (x)
160 mg Fed	Baseline	x	x (x)	x (x)	x (x)
	...	x	x (x)	x (x)	x (x)
320 mg Fasted	Baseline	x	x (x)	x (x)	x (x)
	...	x	x (x)	x (x)	x (x)
640 mg Fasted	Baseline	x	x (x)	x (x)	x (x)
	...	x	x (x)	x (x)	x (x)
Placebo	Baseline	x	x (x)	x (x)	x (x)
	...	x	x (x)	x (x)	x (x)
Albumin, Decrease					
Any Dose	Baseline	x	x (x)	x (x)	x (x)
...	...	x	x (x)	x (x)	x (x)

Notes: The “Maximum Severity Post Baseline” rows indicate the maximum severity experienced by each subject at any timepoint post baseline, including unscheduled assessments.

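### No aggregate laboratory table applies the protocol's treatment-emergent definition, and a Grade 1 result unchanged from baseline prints as Mild in Table 28 but as ONR in Table 23

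*SAP*

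**What the plan says.** **Protocol.** Section 10.5.2 states: "Treatment-emergent abnormal laboratory test results will be identified". It defines these as "tests for which the result was not graded as mild or worse at baseline but graded as mild or worse after dosing", and adds results that were mild at baseline and became moderate or worse. An unchanged Grade 1 meets neither limb. The same section separately asks for laboratory results to be graded and summarised by severity, arm and visit. Exclusion criterion 6 (Section 5.1.2) lets Grade 1 values in: "A laboratory value that is Grade 1 (with the exception of ALT, AST, Total bilirubin, hemoglobin or serum creatinine) will be allowed", provided the investigator judges them not clinically significant.

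**SAP summaries.** Section 9 sets the post-dose maximum: "The most extreme severity grade observed after dosing will be summarized (Maximum Severity Post Baseline) and will include results from unscheduled visits". Section 9.6 plans the "Proportion of subjects with mild, moderate, or severe laboratory results by parameter, Dose Group, and timepoint for CHEM" (Table 28), with Tables 31, 34 and 37 doing the same for hematology, coagulation and urinalysis. The Table 28 footnote says its maximum rows "indicate the maximum severity experienced by each subject at any timepoint post baseline, including unscheduled assessments". The shell also has a Baseline row for each Dose Group.

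**SAP listings.** The notes to Tables 23-26 say that results which meet a grade but "which are not treatment emergent (not worse than baseline, as described in Section 9.6) will be shown as" ONR. SAP 9.6 uses ONR for abnormal results that have no grading range. Listing 12 prints the severity of abnormal results and uses ONR only where no grade applies.

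**AE rule.** SAP 9.6 says a pre-existing laboratory abnormality becomes an AE only if its severity worsens after dosing.

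**The concern.** Laboratory safety is part of the primary endpoint. A reader who wants to know how many subjects at a given dose developed a new laboratory abnormality would turn to the toxicity-grade tables. Their post-dose rows mix new abnormalities with those the subject brought into the trial. The by-subject tables meant for the body of the report handle the same result the opposite way, by removing its grade.

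With 6 active subjects per Dose Group, one or two carried-over grades change the displayed proportion visibly. Coagulation is a relevant case. Prothrombin time and PTT are graded and can be Grade 1 at entry, and Protocol 2.3.1 lists prolongation of both among the animal findings. New and pre-existing prolongation should be separable there.

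**Working it through.** The plan states no figure on this point, so there is nothing to reproduce. The check follows one result through the displays and then sizes the effect.

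**1. One result, four displays.** Take a sodium of 144 mEq/L at baseline and again on Day 4. SAP Table 4 grades 144-145 as Mild.

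| Display | Rule | Day 4 result appears as |
|---|---|---|
| Table 28, Day 4 and maximum rows | grade after dosing, no baseline condition | Mild |
| Table 23 | graded but not worse than baseline | ONR |
| Listing 12 | severity of every abnormal result | Mild |
| AE Tables 17, 19, 20 | AE only if severity worsens | not counted |

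The missing baseline condition in Table 28 is inferred. No sentence says non-emergent grades are to be counted, but Section 9, Section 9.6 and the footnote all describe the observed post-dose grade without qualification.

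**2. What the Baseline row can show.** Suppose a group of 6 has 2 Mild at baseline, 3 Mild at maximum post baseline, and no Moderate or Severe result.
- Both baseline cases persist: 3 - 2 = 1 new case.
- One persists: 3 - 1 = 2 new cases.
- Neither persists: 3 - 0 = 3 new cases.

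The group totals are identical in all three situations. In the first, the maximum row reads 3/6 = 50%, while the treatment-emergent proportion is 1/6 = 17%.

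**3. Size for one parameter.** Each unchanged Grade 1 adds at most 1/6 = 17 percentage points to that parameter's Mild column. If a proportion p of subjects carries an unchanged Grade 1 on an analyte (assumed, because no rate is given), the chance that a group of 6 shows at least one is 1 - (1 - p)^6:
- p = 5%: 1 - 0.95^6 = 26.5%
- p = 10%: 1 - 0.90^6 = 46.9%
- p = 20%: 1 - 0.80^6 = 73.8%

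**4. The chemistry Any Parameter row.** The panel has 24 analytes. Seven have no grades (chloride, triglycerides, total cholesterol, LDL, HDL, total carbon dioxide, GGT). Four are graded but cannot be Grade 1 at entry (creatinine, AST, ALT, total bilirubin). That leaves 24 - 7 - 4 = 13. With an assumed rate q per analyte, independence between analytes and persistence after dosing, the share of subjects counted without any worsening is 1 - (1 - q)^13:
- q = 1%: 12.2%, or 0.73 of 6
- q = 2%: 23.1%, or 1.39 of 6
- q = 3%: 32.7%, or 1.96 of 6
- q = 5%: 48.7%, or 2.92 of 6

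These figures show scale only. Correlated analytes, or Grade 1 values that resolve after dosing, would lower them.

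**The case against.** The planned tables have a good defence. Protocol 10.5.2 itself asks for graded results by severity, arm and visit, with no emergent filter, so Tables 28, 31, 34 and 37 carry out a protocol instruction. For treatment-emergent results the protocol asks only that they be identified, and Tables 23-26 arguably do so subject by subject, since only emergent results keep their grade. The Baseline row and the change-from-baseline tables give context. Pre-existing grades also occur on placebo, which is shown alongside. Criterion 6 admits nothing above Grade 1, so for eligible subjects the carry-over stays in the Mild column. The halting rules turn on SAEs, Grade 2 or higher AEs and QTcF, so no dosing decision depends on it.

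All of that stands, and it rules out some stronger readings:
- A reader might infer that the emergent definition reaches no summary at all. The AE rule in SAP 9.6 carries it into Tables 17, 19 and 20. Only Table 18 excludes graded laboratory AEs.
- A reader might infer that Table 28 cannot be checked against individual data. Listing 12 retains every grade, with change from baseline; only Tables 23-26 remove it.
- A reader might infer that the grade tables breach the protocol. They do not.

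What the defence does not cure is narrower. AE tables are organised by MedDRA term, not by analyte and visit. The Baseline row gives totals that cannot separate new from persistent cases. Change-from-baseline statistics do not count grade shifts. Nothing in the defence explains why ONR carries two meanings in Tables 23-26.

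**Conclusion.** The point holds as a gap in the laboratory displays and a labelling conflict. No aggregate laboratory table uses the protocol's treatment-emergent definition. The maximum-severity rows count Grade 1 results that did not worsen, and the group-level Baseline row does not show which cases are new. Tables 23-26 relabel those results with a code that SAP 9.6 and Listing 12 reserve for ungraded values.

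The firm size is up to 17 percentage points in a parameter's Mild column per carried-over case in a group of 6. In the Any Parameter row a subject counts once however many Grade 1 values are present, and moves out of Mild if any analyte reaches Grade 2, so the increments do not add up across analytes. A reader might take the 12-33% obtained at 1-3% per analyte as a forecast. The documents do not support that: the rates, the independence and the persistence are all assumed.

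This merits correction before the final tables are produced, because it decides whether the primary laboratory summary can separate new abnormalities from pre-existing ones.

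**What to change.** - Keep the by-visit and Maximum Severity Post Baseline rows as planned. Filtering only the maximum row would let it show fewer Mild subjects than the visit rows beneath it.
- Add to Tables 28, 31, 34 and 37 a row for treatment-emergent maximum severity, counting a post-dose grade only if it exceeds that subject's baseline grade. A baseline-by-worst-post-baseline shift table would serve equally well. For Any Parameter, judge emergence within each parameter and direction first, then take the worst. Otherwise a new Grade 1 on one analyte is masked by an old Grade 1 on another.
- In Tables 23-26, print the actual grade with a treatment-emergent flag, and restrict ONR to out-of-range results without a grade.

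The cost is SAP wording, shell edits, slightly more programming and somewhat longer tables. The data are already collected.
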